The choice for which sound processor to be used will be based on a clinical decision, in line with standard care. There will be a choice of sound processors for the trial as listed below.

- 1. Cochlear™ Nucleus® 7 Sound Processor (model number: CP1000)**
- 2. Cochlear™ Nucleus® 8 Sound Processor (model number: CP1110)**
- 3. Cochlear™ Kanso® 2 Sound Processor (model number: CP1150)**

The below information has been taken from their respective instructions for use (Cochlear Limited, 2020a; Cochlear 2022, Cochlear, 2020b).

Indications

The processor works with the implant (see section above) to transfer sound to the ear and, depending on the model, is made up of a processing unit, earhook, coil and cable, magnet and a battery module.

Contraindications

Patients must be suitable for a CI. Please see contraindications for a CI in section above.

Device Descriptions

Cochlear™ Nucleus® 7 Sound Processor (model number: CP1000) and Cochlear™ Nucleus® 8 Sound Processor (model number: CP1110)

The processor can be powered by disposable or rechargeable batteries.

The processor can be controlled by pressing its button, or by using the Cochlear™ Remote Control or the Nucleus® Smart App.

People with certain types of hearing loss can wear the processor in Hybrid™ mode by adding an acoustic component which sends amplified acoustic sound into the ear canal. The Hybrid mode of use is outside of the scope of this trial.

The batteries provide power to the processor. The coil acts as a transformer coupling that transfers energy and data to the implant.

The processing unit comprises:

Two omni-directional microphones for receiving sound.

- An internal telecoil for receiving magnetic fields radiated by neck loops and room loops.
- Custom analogue and digital integrated circuits with digital signal processing and bidirectional wireless communication capabilities.
- A tri-colour visual indication of processor function or problem.
- Control button allowing user control of key features.
- Custom 4-pin connector for coil cable.
- A range of earhooks and specialised retention options.

Cochlear™ Kanso® 2 Sound Processor (model number: CP1150)

The Kanso® 2 sound processor comprises:

- Two omni-directional microphones for receiving sound.
- Custom analogue and digital integrated circuits with digital signal processing and bi-directional wireless communication capabilities.
- Tri-colour visual indication of processor function or problem.

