If a patient has just been through the cochlear implant assessment pathway at a site and has been deemed as ineligible for a cochlear implant on the NHS, they may then be approached for the COACH trial. In this case, the potential participant will be given the EOI and leaflet and allowed time to consider joining the trial. Audiometry and speech scores from their recent assessment may then be used as part of their eligibility assessment for the trial, provided that the assessments were conducted by the participating site and meet the requirements of the trial eligibility assessments. These patients would not need to proceed with the full COACH eligibility pathway and some tests need not be repeated if they have been performed within the last 3 months. An audiometric assessment will need to be repeated at the baseline visit for all participants to ensure they are still eligible for the trial before being randomised. The Phoneme score on the AB Word test in quiet at 70 dBA will not be repeated at the baseline visit, in line with standard clinical practice. This test will only be administered once, either at the consent visit or at a previous clinical appointment, as long as any previous assessment was conducted within 3 months of the consent visit.

Potential participants will also be able to self-refer for trial eligibility assessment, using an online EOI form, or by contacting a member of the trial team for a paper form. Opportunistic recruitment will be facilitated through advertisements placed in clinical areas within recruiting audiology services and PICs. The trial will be advertised through charities such as the Royal National Institute for Deaf People, patient organisations such as the National Cochlear Implant Users Association, National Association of Deafened People and through Twitter, Facebook and social media discussion groups related to HAs and CI candidacy. Advertisements in national press and social media may also be used.

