Following the baseline visit, participants in the intervention arm will attend a meeting of the multi-disciplinary clinical team at which surgical consent will be obtained by a participating CI surgeon to whom that responsibility has been delegated, and at which the MDT will confirm the choice of ear to be implanted based on clinical judgement. All participants will be offered a danalogic GN HA for the ear that will not be implanted. If taken up, the HA will be fitted in line with standard practice at site for a contralateral HA and no later than 6 months following CI activation. All participants will be encouraged to continue to use their HAs in the period before surgery, and in their non-implanted ear following surgery.

It is our expectation that Cochlear implantation surgery occurs within 3 months following randomisation. Unilateral cochlear implantation will be provided in accordance with the quality standards of the British Cochlear Implant Group (BCIG 2018, or latest available version). Participants will attend for surgery on the designated date. This surgery is routinely undertaken on a day case basis in many hospitals, but the participant will be advised as to whether an overnight stay of 1 or more nights will be required or is anticipated.

The choice of CI system will be restricted to the trial devices, which are those manufactured by Cochlear™ Ltd and the most appropriate device for patients with significant residual hearing in the implanted ear. Sites will need to specify the trial devices that each participating surgeon routinely implants. Routine is defined as at least 5 implantations performed per year. NCTU will keep a log of which sites are implanting which devices. Any changes to the pre-specified choice of device will need to be discussed with the NCTU. A surgical protocol will be defined prior to start of recruitment in consultation with CI surgeons, such as those involved in the trial setup, and departures from the protocol will be permitted only where clinically necessary and will be captured via the trial documentation.

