Listening effort and fatigue	FAS total score, EAS total score, LEQ-CI* total score at 1, 3, 6, and 9 months. Scores will be calculated using the algorithms in the questionnaire manuals.
Tinnitus severity	Global 25-item TFI score Global 19-item TFI score (excluding sleep and auditory subscales) TFI scores for 8 subscales All at 1, 3, 6, and 9 months.
Tinnitus loudness	
 • VAS-L rating. Participants mark the loudness of their tinnitus at any point along the numerical scale, with word descriptors utilised as anchor points at 0 for “extremely weak,” 30 for “moderate,” 50 for “strong,” 70 for “very strong,” and 100 for “extremely strong” tinnitus loudness. 
Immediately before and after first treatment activation, and at 1, 3, 6, and 9 months.

Mood	HADS anxiety and depression subscale scores at 1, 3, 6, and 9 months.
Hearing-specific quality of life	NCIQ total and six subdomain scores YBHRQL binaural utility value HHIA total score and two subscale (emotional and social/situational) scores All at 1 month, 3 months, 6 months, and 9 months.
Health-related quality of life	HUI3 multi-attribute utility value, EQ-5D-5L health utility value using EQ-5D-3L UK value set ICECAP-A tariff value All at 1 month, 3 months, 6 months, and 9 months.
Global ratings of change	Likert scale ratings of change (7 points from much worse to much improved) in hearing and quality of life relative to two anchor points (immediately prior to first treatment activation; since the last trial appointment) at 1, 3, 6, and 9 months.
Audiometric thresholds	Unaided audiometric thresholds at first treatment activation and at 3, 6 and 9 months.

Outcome Measure	Derivation
	Aided audiometric thresholds at first treatment activation and at 3 and 9 months.

*Data only to be collected using LEQ-CI questionnaire once licence is in place

Assessment of safety

Safety data, including number of expected AEs and SAEs and unexpected related SAEs will be summarised with descriptive statistics according to the treatment the participant received, irrespective of randomisation; where anyone received more than one treatment (e.g., HA then CI) these will be summarised separately. Where a participant did not receive their allocated treatment but had an expected AE, or SAE this will be indicated.

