4. disease or disorder being studied, or sign or symptom associated with the disease or disorder unless more severe than expected for the participant's condition.
5. overdose of concurrent medication without any signs or symptoms.
6. expected AE as listed below.

Expected adverse events

The treatments provided to both intervention arms are widely available within the NHS, used in standard care and considered to be safe. Known adverse events (listed in the table below) are related to their respective trial interventions. These events are secondary outcomes and will be collected as part of the eCRF. The number of occurrences of expected AEs and SAEs will be regularly reviewed throughout the trial by the TMG and the DMC.

Expected AE	Expected SAE
Related to Cochlear Implantation (intervention arm only)	
Facial nerve stimulation (temporary)	Facial nerve stimulation (chronic)
Patient reported decreased hearing ability or loss of residual acoustic hearing (temporary or permanent)	The inability to use the implant or a hearing aid in that ear
Vestibular dysfunction (temporary)	Vestibular dysfunction (chronic)
Perception of non-auditory sensations (temporary or permanent)	Infection requiring hospitalisation (e.g., meningitis and the need for vaccination)
New onset or exacerbation of pre-existing tinnitus	Any surgical complication that requires hospitalisation
Altered taste	Need for revision surgery, reimplantation or explantation
Facial weakness	Subdural injury
Acute otitis media or any other infection treated by oral antibiotics	Chronic pain in or around the implant site or hearing aid
Perilymph fistula	

Expected AE	Expected SAE
Concurrent cerebrospinal fluid (CSF) leakage	
Subcutaneous haematoma	
Unsatisfactory device insertion (e.g., misplacement of electrode array, incomplete electrode insertion, tip fold-over)	
Failure of component parts	
Related to Hearing Aids (intervention and comparator arms)	
Ear infection	None
Exacerbation of eczema	

Serious Adverse Events

A Serious Adverse Event (SAE) is any adverse event occurring following trial mandated procedures that results in any of the following outcomes:

1. Death
2. A life-threatening adverse event
3. Inpatient hospitalisation or prolongation of existing hospitalisation
4. A disability / incapacity
5. A congenital anomaly in the offspring of a participant

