All adverse events (AEs) will be recorded as they are reported whether spontaneously volunteered or in response to questioning about wellbeing at trial visits. The questioning about AEs will cover the current visit as well as the period of time between the previous and the current visit. A note of any concomitant medication will also be made, where available, so that a full assessment of the AE can be made.

Abnormal test results that are deemed clinically significant by the investigator and that lead to a change or temporary or permanent discontinuation in the use of the device or require intervention or diagnostic evaluation to assess the risk to the subject will be recorded as adverse events and instigate further investigation and follow up as appropriate.

All AEs and SAEs will be documented in the subject’s medical records. As both trial interventions are well established and have extensive safety profiles already available, only related, or suspected to be related, SAEs will be documented on the eCRF.

For related, or suspected to be related, events, participants should be followed up until resolution or stabilisation of the event. Follow-up information should ideally be provided on a new SAE form.

Participants will be asked to contact the trial site immediately in the event of any SAEs. The Chief Investigator or nominated deputy shall be informed immediately of any related, or suspected to be related, serious events and shall determine seriousness and relationship in conjunction with any treating medical practitioners.

SAEs will be recorded and reported to the REC and Sponsor as part of the annual progress reports.

SAEs will be reported within the statutory timeframes to the REC as stated below. The Chief Investigator will be responsible for all adverse event reporting.

The NCTU will also notify the trial funder by email from the Chief Investigator to [name] [name], Global Head of Clinical Affairs, Cochlear™ Ltd, [contact] and [name], Clinical Portfolio Manager, Cochlear™ Ltd, [contact] of any serious adverse events at the time of regulatory reporting.

The funder will notify the University by email to [contact] (cc to [contact]) of any reportable events involving devices (Cochlear™ or GN Hearing UK) at the time of reporting to the MHRA, or any other relevant regulatory authorities of any new information which becomes available to them as device manufacturers which could affect the safety of trial participants.

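### The expected-event row for residual hearing can be read as patient report only and is not linked to the unaided audiograms, so the safety count may understate the loss

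*Protocol*

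**What the plan says.** The Adverse Events section, under Expected adverse events, lists for the implant arm only "Patient reported decreased hearing ability or loss of residual acoustic hearing (temporary or permanent"). It is the only row in the table that opens by naming the patient as the source. No ear, frequency set, size of change or reference visit is given. The nearest serious event in the table is functional: "The inability to use the implant or a hearing aid in that ear". On collection, the section says "These events are secondary outcomes and will be collected as part of the eCRF", and that the trial management group and the data monitoring committee will regularly review how often listed events occur.

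On use of the implanted ear, the sound processor description says "The Hybrid mode of use is outside of the scope of this trial". The Intervention group section encourages hearing-aid use before surgery "and in their non-implanted ear following surgery".

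On measurement, the Recruitment section says "An audiometric assessment will need to be repeated at the baseline visit for all participants", and Appendix 1 marks audiometry at baseline. The outcome derivation table lists "Unaided audiometric thresholds at first treatment activation and at 3, 6 and 9 months". Under Statistics, Methods, audiometric thresholds are summarised descriptively, without a between-arm model.

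**The concern.** Two different things share one row. A felt decrease in hearing is a symptom. Loss of residual acoustic hearing in the operated ear is a finding that an audiogram shows. Once the implant is switched on the two can part company: the participant may hear better overall while acoustic hearing in that ear has gone, and has little occasion to notice it.

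This matters more here than in a conventional implant population. The background section explains that these patients are outside current candidacy partly because their residual hearing lets them benefit from hearing aids. The Intervention group section expects significant residual hearing in the ear to be implanted, and the public involvement section records residual hearing as a patient concern. Safety is a stated secondary objective. A count of this harm that varies with who notices and who records it is a weak basis for committee review and for the benefit-risk judgement.

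**Working it through.** **1. The plan's own figures.** The protocol states no rate or count for this event, so there is none to reproduce. The only number used below is the arm size: 55 / (1 − 0.15) = 64.7, rounded up to 65 per arm, as the sample size section states. Safety data are summarised by treatment received, so the number actually implanted may differ from 65.

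**2. Does another rule capture an unnoticed loss?**
- The list of what is not an adverse event excludes the listed expected events, so the general definition does not pick the loss up.
- The rule on abnormal test results, under Recording and Reporting of Adverse Events, needs clinical significance plus results "that lead to a change or temporary or permanent discontinuation in the use of the device" or that require intervention or diagnostic evaluation. A threshold shift in an ear used only electrically need not meet it. The opening of that section also says that it does not pertain to listed expected events.
- The paired serious event asks whether the implant or a hearing aid can be used in that ear. Someone using the implant does not meet it, whatever the audiogram shows.

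**3. Are the data there?** Yes. Unaided thresholds are scheduled before randomisation, at activation (T0) and at 3, 6 and 9 months. In an implanted participant T0 follows surgery, so only the baseline audiogram can serve as the reference. The derivation row starts at T0 and names no change from baseline.

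**4. When could a loss be masked?** Only after switch-on. Between surgery and activation there is no electrical hearing, and Appendix 1 marks both adverse effects and audiometry at T0. A loss present by then may be noticed or recorded at that visit.

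**5. Illustration of size, on assumptions only.** Let p be the true share of 65 implanted participants with loss, and s the share of those losses that reach the event count. Counted = 65 × p × s. Neither p nor s is in the documents; both ranges are assumed.

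| p | True losses (65 × p) | s = 25% | s = 50% | s = 75% | s = 100% |
|---|---|---|---|---|---|
| 20% | 13 | 3.25 | 6.5 | 9.75 | 13 |
| 40% | 26 | 6.5 | 13 | 19.5 | 26 |
| 60% | 39 | 9.75 | 19.5 | 29.25 | 39 |

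The proportion missed is 1 − s at every p: 75% at s = 25%, and zero at s = 100%. The table therefore only restates the assumed reporting rate. It shows that the count depends on s, and a threshold-derived count would not.

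**The case against.** The strongest reply is that the row need not mean patient report only. Its opening words may qualify just the first half, leaving loss of residual hearing open to clinician entry. The synopsis supports this, since it defines the safety outcome as complications reported by participants and by investigators, with medical notes available if needed. Listed events are also said to be recorded in the notes, collected in the eCRF and monitored centrally. This stands, and it rules out saying that the event is counted by self-report alone. It does not cure the row: a wording that supports two readings and gives no criterion can be completed differently from site to site.

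Second, the loss is measured objectively and will be reported. Unaided thresholds are a listed outcome in both arms, and the descriptive summaries are not limited to means. This also stands: the harm is not hidden from the trial report. But a summary of thresholds at each visit need not give the number of participants who lost hearing, and it does not feed the event count that the committees review.

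Third, a cut-off in decibels and a derived percentage are commonly left to the statistical analysis plan. Agreed, and their absence is not the point. The event wording and its collection are set in the protocol, and a later analysis plan cannot repair inconsistent entry.

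A reader might go further and infer that the count will certainly be too low, by some stated percentage. The documents do not support that. Investigators may record the loss, masking cannot operate before activation, and participants who worry about residual hearing may be alert to its loss.

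**Conclusion.** The point holds as a defect of wording and linkage. One row mixes a symptom with a measurable loss, can be read as patient report only, and ignores audiograms that the trial already takes. The safety count may understate loss of residual hearing, and it will depend on who records it. The direction is plausible rather than certain. It rests on the implanted ear not being used acoustically after activation and on some losses going unrecorded. The size cannot be derived from the documents. The primary analysis and the sample size are unaffected. The change is worth making because this harm is central to benefit-risk in this population and the remedy is cheap.

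**What to change.** Split the row in the expected-event table into (a) patient-reported decrease in hearing and (b) loss of residual acoustic hearing in the implanted ear. For (b):

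- Derive it from unaided thresholds at T0, 3, 6 and 9 months against the pre-randomisation baseline audiogram, not against T0.
- Use a size of change and a set of frequencies that the investigators fix in advance.
- Count no response at the audiometer limit as loss only at frequencies that were measurable at baseline. Otherwise frequencies already at the limit before surgery would count as new losses.
- Report number and percentage in the safety tables beside the patient-reported count.
- Give the same threshold-shift count in the hearing-aid arm. The protocol itself notes that hearing loss is often progressive in these patients, and a count in one arm cannot separate progression from surgical loss. That arm has no implanted ear, so the ear or ears to be compared must also be fixed in advance.

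The cost is one reworded table row, one derived variable, a pre-set cut-off and an extra line in the safety table, all from measurements already scheduled. The downside is small: the reported event rate in the implant arm may be higher.

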A distinction is drawn between serious and severe AEs. Severity is a measure of intensity whereas seriousness is defined using the criteria above. Hence, a severe AE need not necessarily be serious.

Important medical events that may not result in death, be life-threatening, or require hospitalisation may be considered a SAE when, based upon appropriate medical judgment, they may jeopardize the patient or participant and may require medical or surgical intervention to prevent one of the outcomes listed in this definition.

Events deemed by the investigator to be related to COVID-19 infection will not be reportable.

If an adverse event, *not listed as expected AEs above*, meets, or potentially meets, the SAE criteria it will be assessed for seriousness, and causality.

Causality

Not related or improbable: a clinical event including laboratory test abnormality with temporal relationship to trial device which makes a causal relationship incompatible or for which other treatment, drugs, chemicals or disease provide a plausible explanation. This will be counted as “unrelated” for notification purposes.

Possible: a clinical event, including laboratory test abnormality, with temporal relationship to trial device which makes a causal relationship a reasonable possibility, but which could also be explained by other treatments, devices, drugs, chemicals or concurrent disease. This will be counted as “related” for notification purposes.

Probable: a clinical event, including laboratory test abnormality, with temporal relationship to trial device which makes a causal relationship a reasonable possibility, and is unlikely to be due to other treatments, devices, drugs, chemicals or concurrent disease. This will be counted as “related” for notification purposes.

Definite: a clinical event, including laboratory test abnormality, with temporal relationship to trial device which makes a causal relationship a reasonable possibility, and which can definitely not be attributed to other causes. This will be counted as “related” for notification purposes.

Recording and Reporting of Adverse Events

The below section **does not pertain to** expected AEs and SAEs (included in table of expected events above) which do not require expedited reporting with a trial SAE form. These events are secondary outcomes recorded in medical notes and collected as part of the eCRF, that will be routinely centrally monitored and reported.

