SAE Reporting Procedure for Unexpected SAEs – At Site

On becoming aware that a participant has experienced an SAE, the Investigator (or delegate) must complete, date and sign an SAE Form. The form should arrive at the NCTU as soon as possible and no later than **24 hours** after first becoming aware of the event:

To report an SAE, email the SAE Form to: [contact]

On receipt, NCTU will allocate each SAE a unique reference number which will be forwarded to the site as proof of receipt. If confirmation of receipt is not received within 1 working day, the site will contact the NCTU. The SAE reference number should be quoted on all correspondence and follow-up reports regarding the SAE and filed with the actual SAE in the ISF.

For SAE forms completed by someone other than the local PI, the Investigator will be required to countersign the original SAE Form to confirm agreement with the causality and severity assessments. For sites where the PI is an audiologist, the responsibility for causality assessment and sign off of SAEs will be delegated to the lead surgeon at site. The form should be returned to NCTU and a copy kept in the ISF.

Investigators should also report SAEs to their own Trust in accordance with local practice.

SAE Reporting Procedure for Unexpected SAE – NCTU

On receipt, NCTU will allocate each SAE a unique reference number which will be forwarded to the site as proof of receipt within 1 working day. The SAE reference number will be quoted on all correspondence and follow-up reports regarding the SAE and filed with the SAE form in the TMF.

On receipt of an SAE Form, seriousness and causality will be determined independently by the Chief Investigator, or their delegate, responsible for determining causality assessments. The Chief Investigator's delegate will review all SAEs reported by the Chief Investigator's host site. An SAE judged by the Investigator, Chief Investigator or their delegate to have a reasonable causal relationship with the trial treatment will be regarded as a related SAE. The Chief Investigator (or their delegate) will also assess all related SAEs for expectedness. If the serious event is unexpected (i.e., is not defined in the protocol as an expected event) it will be classified as an unexpected and related SAE.

SAEs

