. Unexpected serious adverse events related to the trial intervention will be reported within the timeframes to the REC as stated below. The Chief Investigator shall be responsible for all adverse event reporting.

A serious adverse event that is unexpected in its severity and seriousness *and* deemed directly related to or suspected to be related to the trial treatment shall be reported to the ethics committee that gave a favourable opinion as stated below.

The event shall be reported immediately of knowledge of its occurrence to the Chief Investigator or their delegate.

The Chief Investigator (or their delegate) will:

- Assess the event for seriousness, expectedness and relatedness to the trial intervention.
- Take appropriate medical action, which may include halting the trial and inform the Sponsor of such action.

- If the event is deemed related to the trial treatment shall inform the REC within 7 days of knowledge of the event.
- Shall, within a further 8 days send any follow-up information and reports to the REC.
- Make any amendments as required to the trial protocol and inform the REC as required.

Reporting to the Research Ethics Committee

Unexpected and Related Serious Adverse Events

NCTU will support the Chief Investigator to ensure that the reporting for all events categorised as unexpected and related SAEs to the REC will be completed within 15 days.

Adverse Events

The REC will be notified immediately if a significant safety issue is identified during the trial. However, reporting of adverse events that are not deemed serious is not required for this trial.

Investigators

Details of all unexpected and related SAEs and any other safety issues which arises during the trial will be reported to PIs. A copy of any such correspondence should be filed in the ISF.

Data Monitoring Committee

The independent DMC will review outcome data at regular intervals throughout the trial, in addition to reported SAEs.

ETHICAL AND REGULATORY ASPECTS

ETHICS COMMITTEE AND REGULATORY APPROVALS

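### One expected-SAE row covers surgical complications by hospital admission alone, so an unforeseen complication needing admission is classed as expected and bypasses the SAE form

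*Protocol*

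**What the plan says.** All places are in the protocol.

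- **Expected adverse events.** The table is introduced with the statement that "Known adverse events (listed in the table below) are related to their respective trial interventions". In the Expected SAE column for cochlear implantation, one row reads "Any surgical complication that requires hospitalisation".
- **Serious Adverse Events.** One criterion that makes an event serious is "Inpatient hospitalisation or prolongation of existing hospitalisation". Death, threat to life and disability are separate criteria.
- **Recording and Reporting of Adverse Events.** The section opens by excluding "expected AEs and SAEs (included in table of expected events above) which do not require expedited reporting with a trial SAE form". It adds that these events are still noted in the medical records, collected in the eCRF and monitored centrally.
- **SAE Reporting Procedure for Unexpected SAE – NCTU.** The test is "If the serious event is unexpected (i.e., is not defined in the protocol as an expected event"; a related event that passes it becomes an unexpected and related SAE.
- **SAEs.** The sentence on reporting to the ethics committee uses other words: "A serious adverse event that is unexpected in its severity and seriousness".
- **Assessment of safety.** The planned safety result is that the "number of expected AEs and SAEs and unexpected related SAEs will be summarised with descriptive statistics". The same section also plans totals and types of all AEs and SAEs, by event.

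**The concern.** A list of expected events should hold events whose nature is already known. Most entries in the Expected SAE column do so: chronic facial nerve stimulation, chronic vestibular dysfunction and subdural injury are examples. This row describes an open class, fixed by where the event came from and by its consequence. A complication that nobody had in mind when the table was written fits it as well as a familiar one does.

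Surgery is the invasive part of the trial, and participants fall outside current NICE candidacy criteria. The expedited route exists to get an unfamiliar harm looked at as a single case, quickly, by someone other than the reporting site. The row removes that step for a class of events in which it could matter, and it puts the wrong label on them in the safety results.

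**Working it through.** No arithmetic applies. The point depends on no rate, sample size or effect size, so the check is to follow the row through the rules.

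1. **What the row tests.** It has two conditions: the event is surgical, and it requires hospitalisation. The second repeats a seriousness criterion ("Inpatient hospitalisation or prolongation of existing hospitalisation"). Nothing in the row asks whether the event is known, although the table is introduced as a list of known events.

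2. **How expectedness is decided.** The NCTU procedure equates unexpected with absence from the protocol's list ("If the serious event is unexpected (i.e., is not defined in the protocol as an expected event"). Nature and severity play no part. An unforeseen surgical complication needing admission is on the list through this row, so it is expected.

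3. **What follows from being listed.** The recording and reporting section is disapplied for "expected AEs and SAEs (included in table of expected events above) which do not require expedited reporting with a trial SAE form". The steps that fall away are the form reaching NCTU within 24 hours, the Chief Investigator's independent assessment of seriousness, causality and expectedness, and the report of unexpected related SAEs to the REC (7 days, plus a further 8 for follow-up, within 15 days overall). The definition of an AE also excludes an "expected AE as listed below". Whether that wording reaches the Expected SAE column is unclear, but the chain does not need it.

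4. **Whether the other wording brings the event back.** "A serious adverse event that is unexpected in its severity and seriousness" would allow a listed event to be unexpected because of its severity. It is a different test from the one in step 2, and it sits within the part disapplied in step 3. The Chief Investigator's assessment starts on receipt of an SAE form, and none is required for a listed event. The two tests contradict each other, and the list-only test acts first.

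5. **What the analysis then shows.** The event is counted as an expected SAE and is missing from the unexpected related SAEs.

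Applying steps 1 to 3 to four kinds of surgical event:

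| Event | In the table? | SAE form required? |
|---|---|---|
| Complication named in its own row | Yes | No |
| Unforeseen complication requiring admission | Yes, through this row only | No |
| Unforeseen event, unnamed, serious only through death, threat to life or disability, with no admission required | Not literally covered | Yes |
| Unforeseen complication that only prolongs an existing stay | Unclear: the row does not mention prolongation, the SAE criterion does | Unclear |

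The second line is the misclassification. The last two show where the row stops.

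**The case against.** The strongest case against is that little is hidden. Listed events go into the eCRF, are monitored centrally, and have their numbers reviewed regularly by the TMG and DMC. The totals by event keep them in the results. Separately, the protocol promises immediate notice to the REC of a significant safety issue, and notice to principal investigators of other safety issues; neither promise is tied to the list. Listed events are already treated as related, so a causality review would add little. Other rows also name consequences (revision surgery, inability to use the device), and introducing the table as known events suggests a narrower intent.

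Most of this stands, and it limits the consequences. It does not repair the classification. The stated review of listed events is of numbers of occurrences. The guaranteed minimum meeting frequency is every two months for the TMG and once a year for the DMC, against 24 hours for a form. The general safety clauses work only once someone has recognised an issue, and the form is the step designed for that. The narrower intent is not what the row or the list-only test says.

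A reader might infer more than the text supports:

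- **That the REC and other sites would never hear of a new surgical harm.** The general safety clauses contradict this.
- **That the class of unexpected related SAEs is close to empty for implantation.** Events serious through other criteria, without a required admission, are not literally covered by the row.
- **That the arms cannot be compared on safety.** The summaries are descriptive and by treatment received, the totals include these events, and different lists for surgery and hearing aids follow from the design.
- **That the problem can be sized from an overall rate of surgical admissions.** The protocol gives no rate, and such a rate would mix foreseen with unforeseen complications.

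**Conclusion.** The point holds as a misclassification with limited consequences. Read literally, the row, the list-only test and the exemption together class an unforeseen surgical complication requiring admission as expected, and this conflicts with the sentence that judges expectedness by severity and seriousness. What is lost is prompt case-level review, the Chief Investigator's judgement of expectedness, the REC report of unexpected related SAEs and the correct label in the safety summary. Visibility as such is not lost.

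No number of affected events can be given from the protocol. The conclusion assumes that sites apply the table as worded; a site that read it as covering only familiar complications might still send a form, but the text does not require it. The passages should be reconciled, because this is a stated rule that yields a wrong classification and is cheap to correct.

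**What to change.** Make one of two changes by amendment:

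- **Replace the row** with the surgical complications that the sponsor and the implanting surgeons regard as foreseen, each named.
- **Or keep the row and add a reconciling clause** covering the table, the exemption and the NCTU test. It would state that a surgical SAE whose nature or severity is not described in the table goes on an SAE form within the existing 24 hours, that the Chief Investigator or delegate judges its expectedness, and that hospitalisation alone does not make an event expected.

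Either way, use one definition of expectedness in the NCTU procedure and in the paragraph on reporting to the ethics committee, so that the count of unexpected related SAEs rests on it.

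The cost is one table row or one short clause, alignment of the cross-references, notice to sites, and a few additional SAE forms. Outcomes, sample size and the analysis model are unaffected.
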